Study Rationale	
• Deficits in motivation and pleasure, together referred to as anhedonia, are implicated in a number of psychiatric illnesses, including mood and anxiety disorders, substance-use disorders, schizophrenia, and attention-deficit/hyperactivity disorder.• Anhedonia is often one of the most difficult psychiatric symptoms to treat and thus represents a critical endophenotype and vulnerability factor for a range of psychiatric disorders.• Individuals with anhedonia exhibit impaired responsivity of the mesocorticolimbic system, yet the translation of these findings to clinical practice has been limited: many pharmacological treatments do not target this system directly and many psychosocial interventions do not focus on improving motivation and pleasure.• The overall goal of the proposed research is to investigate the viability and efficacy of a novel transdiagnostic and non-pharmacological treatment for anhedonia called Behavioral Activation Therapy for Anhedonia (BATA).• This intervention is designed to restore reward motivation and reward responsiveness in individuals with clinically impairing anhedonia.• Our neurobiological target for this intervention is mesocorticolimbic activation during reward anticipation and reward outcomes measured using fMRI.
Study Objective(s)	
In this trial, we will test whether BATA alters brain activation in target engagement regions during reward processing in outpatients with impairing anhedonia who will receive BATA or an active comparison treatment, Mindfulness Based Cognitive Therapy (MBCT), and who complete fMRI scans before and after treatment.
 
Aim 1: To evaluate whether BATA produces changes in neural responses to reward anticipation and reward outcomes using high field fMRI that exceed our a priori target engagement criteria (right caudate nucleus (CN) activation during reward anticipation and decrease rostral anterior cingulate cortex (rACC) activation during reward outcomes) and exceed changes due to an active comparison treatment.
 
Aim 2: To evaluate the effects of BATA versus an active comparison treatment on anhedonic symptoms.

Test Article(s) (If Applicable)	
Behavioral Activation Treatment for Anhedonia (BATA): We have modified Behavioral Activation Treatment for Depression to create Behavioral Activation Treatment for Anhedonia (BATA) which we will evaluate in this study by comparing its effects on brain functioning relative to treatment with Mindfulness-Based Cognitive Therapy (MBCT).

Study Design	Following a phone/online screen and an initial assessment session to confirm eligibility, participants will complete a baseline fMRI session at the UNC Biomedical Research Imaging Center (BRIC). They then will be randomized to receive a 15-week course of BATA (50%) or a 15-week course of Mindfulness Based Cognitive Therapy (MBCT) (50%) administered at Duke University Medical Center (DUMC). Both groups will receive pre- and post-treatment scans as well as two mid-treatment scans (weeks 8 and 12) to evaluate treatment BATA dose.
---------------------	--

Subject Population	Inclusion Criteria
key criteria for Inclusion and Exclusion:	
 1. 18-50 years old and treatment seeking; 2. SHAPS scores ≥ 20, corresponding to clinically significant anhedonia; 3. Clinician's Global Impression Scale-Severity score (CGI-S) ≥ 3 to assure a clinically impaired sample; 4. Seeking treatment for anhedonia (i.e., referred from an outpatient clinic or responded to an advertisement for anhedonia treatment; endorses desire for treatment during screening).

Exclusion Criteria

5. Those for whom medication management is the primary gold-standard treatment, including those with bipolar disorder/mania, schizophrenia spectrum, and other psychotic disorders;
6. Prior treatment with behavioral activation therapy for depression or mindfulness-based treatments (those with exposure to other forms of psychotherapy, e.g., supportive therapy, will be eligible);
7. Those who may have difficulty understanding the cognitive components of BATA, including those with intellectual disability, neurocognitive disorders, and dissociative disorders;
8. Feeding and eating disorders which may have confounding effects on the BOLD fMRI signal;
9. Substance Use Disorders given confounding effects of substances of abuse on the BOLD fMRI signal;
10. Suicidal intent and plan;
11. Psychotropic medication use in the past 4 weeks (8 weeks for fluoxetine) and/or current psychotherapy. Participants must be medication-free at study entry; study personnel will not supervise medication taper for the purpose of the study, but those who taper under the supervision of their regular provider will be eligible;
12. Currently pregnant, as measured by urine pregnancy screen immediately before MRI scans;
13. Positive urinalysis screen for cocaine, marijuana, opiates, methadone, amphetamines, and benzodiazepines (conducted on-site via Biosite Triage Meter Plus) at study entry.
14. No neurological conditions (e.g., history of stroke, seizure, or TBI);
15. Contraindications for 7T imaging (criteria are more stringent than for 3T imaging): Metal in the body, dental work that is not fillings or gold, any tattoos, any metal in the body, any metal injury – especially those to the eyes, any other type of implant unless they are 100% plastic.

Number Of Subjects	60 subjects will be randomized such that half will receive BATA and half will receive MBCT.
---------------------------	---

Study Duration	Approximately 16 weeks
Study Phases	(1) Phone/online Screening : initial screening for eligibility.
Screening	(2) In-Person Screening : further screening for eligibility and consent
Study Treatment	(3) Baseline fMRI
Follow-Up	(4) Initiate up to approximately 15 weeks of therapy (experimental treatment (BATA) or comparison treatment (MBCT)) (5) Mid-treatment fMRI scans at approximately weeks 8 and 12. (6) Post-treatment fMRI scan.
Efficacy Evaluations	(1) fMRI activation in right CN during reward anticipation and rACC during reward outcomes (2) Anhedonia severity (SHAPS scores)
Pharmacokinetic Evaluations	N/A
Safety Evaluations	1) 7T MRI safety screening form completed before each scan session 2) Columbia-Suicide Severity Rating Scale (C-SSRS) completed if a subject endorses suicidal thoughts at therapy visits.
Statistical And Analytic Plan	Aim 1: Primary Endpoint (fMRI) : Only patients who completed at least two therapy sessions will participate in post-treatment assessments. We will compare fMRI activation in regions of interest at pre- and post-treatment. The design is a 2 (BATA vs MBCT) X 2 (CN, rACC) X 2 (pretreatment vs post-treatment) ANCOVA testing the change from pre- to post-treatment as moderated by treatment group and brain region in the outcome variables. Aim 2: Secondary Endpoint : To evaluate the efficacy of BATA, relative to MBCT, for treating anhedonia, we will test for differential change over time between those who receive BATA and those who receive MBCT post-treatment. We will use an intent-to-treat (ITT) analysis for patients who receive BATA relative to those who don't. The ITT model will be a repeated-measures ANCOVA with effects for treatment condition (BATA, MBCT), outcome measure (SHAPS), time (pre-treatment, post- treatment) and their interactions. The interaction tests will assess mean differences at each time point as well as differences in the degree of change between the groups. This also provides tests of each group relative to their baseline scores. We will include gender and age as covariates in these models.
DATA AND SAFETY MONITORING PLAN	We will have an independent Data Safety Monitoring Board (DSMB) that will meet twice per year to review any adverse events as well as participant accrual and adherence/drop-outs. The members of the DSMB will be responsible for safeguarding the interests of study participants, assessing the safety of all study procedures, and monitoring the overall conduct of the study. This committee will serve as an independent advisory group to the study investigators and will provide recommendations about starting, continuing, and stopping the study.

1 BACKGROUND AND RATIONALE

1.1 Introduction

The goal of this project is to evaluate a novel transdiagnostic treatment for anhedonia. Anhedonia, the loss of motivation and pleasure for enjoyable activities, is a transdiagnostic symptom associated with significant functional deficits in social and occupational domains. In mood disorders, anhedonia is associated with risk for future depressive episodes, a more chronic illness course, and poorer treatment response to both pharmacologic and neurostimulation interventions. Outside of mood disorders, anhedonia is associated with greater risk of anxiety disorders and reduced cognitive and social functioning as well as quality of life. Across psychiatric disorders, deficits in approach motivation (reduced reward valuation and willingness to work for rewards) and initial response to rewards (reduced hedonic responses to pleasurable stimuli) have been proposed to subserve anhedonic symptoms by reducing approach behaviors and pleasurable experiences, as well as subsequent opportunities for positive reinforcement.

The mechanistic objective of this proposal is to explicate the brain-behavior relations between anhedonia and the dimensional constructs of approach motivation and initial responsiveness to reward. This will be achieved by measuring mesocorticolimbic target engagement before and after BATA treatment. In our previous collaborative work (MH094781 & MH078145) we delineated the neurobiological mechanisms of deficits in these dimensional RDoC constructs, including altered mesocorticolimbic activation that subserves approach behaviors towards biologically meaningful goals and hedonic responses to pleasurable stimuli, changes in activation of these brain regions after behavioral activation psychotherapy, and linkages between functioning of mesocorticolimbic systems and behavioral activation treatment outcomes. The goals of the current study are to extend these lines of inquiry into first an experimental therapeutics study and then a future clinical trial in a transdiagnostic sample characterized by anhedonia.

1.2 Name and Description of Investigational Product or Intervention

Behavioral Activation Treatment for Anhedonia (BATA): We have modified Behavioral Activation Treatment for Depression to create Behavioral Activation Treatment for Anhedonia (BATA). Treatment in the R61 phase will consist of ~15 weekly 45-minute sessions. Session 1 provides orientation and psychoeducation on anhedonia, and activity monitoring is introduced. Sessions 2-3 include structured values assessments of 10 life areas (e.g., Family Relationships, Employment/Career) to enhance motivation for sustained behavior change and to clarify goals. Following goals clarification, an activity hierarchy is developed, establishing a set of idiographic behavioral targets across life areas prioritized by ease of implementation to scaffold task engagement during the course of treatment. Session 4 focuses on reduction of avoidance. Sessions 5 and above assess completion of goals from the previous sessions, troubleshoot barriers to goal completion, and assign goals for the coming weeks. Inherent in this structure is therapist assistance in setting achievable goals, which is often impaired in the context of anhedonia. Embedded in the review of goal completion is heightened awareness of anhedonia and identification of behaviors that are associated with greater positive response in the form of subjective importance and enjoyment. Those behaviors then form the basis of goals for the following weeks. The therapist uses motivational techniques to elicit goal-directed behaviors outside session including tying goals to the patient's identified values, open-ended questioning and reflective listening, and functional analysis to select behaviors maximally likely to achieve the patient's goals. Increased positive affect and decreased negative affect are theorized to result from increased contact with potential reinforcers through reduced behavioral avoidance. Maladaptive behaviors such as avoidance decrease the effectiveness of positive events in shaping future behavior, weakening the learned association between adaptive behaviors and positive outcomes. In this way, the overarching goal of BATA is to encourage the patient to engage in activities that increase contact with personally relevant, values-consistent reinforcers, thereby strengthening links between environmental engagement, positive mood, and future approach-oriented behaviors. Several specific new components are included in BATA: in Session 1, content specific to depression is removed and additional psychoeducation about anhedonia and response to rewards is provided. This includes education about

anticipatory versus consummatory anhedonia, positive versus negative reinforcement, and how anhedonia can foster avoidance. Activity monitoring is streamlined to reduce monitoring effort for low-motivation patients. Sessions 5 includes a focus on increased frequency of initiation of new behaviors to target motivation. In Session 6, once novel behaviors are established, additional exercises will be introduced to increase present-moment savoring as a means to target pleasure.

Mindfulness Based Cognitive Therapy (MBCT): BATA will be compared to MBCT, chosen because its mechanisms of action are hypothesized to impact different brain mechanisms than BATA. Mindfulness is nonjudgmentally bringing awareness and acceptance to one's present-moment experience. Mindfulness-based interventions have demonstrated efficacy for treatment of diverse psychological symptoms including depression. Several studies have shown that MBCT facilitates decentering from negative states, including rumination, cognitive reactivity to emotion, and negative bias. While mindfulness can enhance positive emotions and increase the frequency of positive affect, these effects are mediated by reduction of perseverative negative thinking. This suggests that MBCT exerts its clinical effects via reductions in negative affect, not increases in motivation of pleasure. This is consistent with findings showing mindfulness is associated with activation in sensory regions and reduced amygdala reactivity to negative stimuli rather than increases in striatal reward processing regions.

To control for nonspecific factors in BATA including clinician contact, MBCT will be administered in an individual format. MBCT for individual treatment is empirically supported for a number of forms of psychopathology. Individualized adaptations of MBCT share primary components of the traditional program, including instruction and in-session practice of meditative exercises, didactics, and home practice. MBCT will be comprised of 15 weekly 45-minute sessions. Sessions will begin with practice and discussion of a mindfulness meditation exercise, and then include: discussion of home practice, introduction to a new exercise and/or psychoeducational topic, and explanation of home practice for the coming week. Initial sessions will focus on practice and discussion of core meditation exercises to build mindfulness skills. Later sessions will focus on generalizing learned skills to cope with stressors and mood shifts. Psychoeducational content will center on identifying connections between negative thoughts, emotions, and sensations, recognizing triggers of emotional events, and developing an "action plan" to reduce stress-related symptoms. At the end of each session, participants will receive handouts that summarize the meditative exercise and/or psychoeducational content covered each week. Participants will also be asked to practice meditation exercises at home for 30 minutes each day and track practice time. Homework and logging are included to control for homework and monitoring components of BATA. Participants will receive guided meditation CDs to aid in home practice. Adherence will be monitored by tracking attendance; compliance of home practice will be monitored by evaluating frequency and duration of practice on weekly homework logs.

1.3 Non-Clinical and Clinical Study Findings

Potential Risks

BATA: BATA works with cognitions and emotions, some of which are distressing and difficult; they include a variety of exercises, which can be uncomfortable. It is possible that some participants receiving BATA may get worse, novel symptoms may emerge. Rd reviews have concluded that between 3% and 10% of psychotherapy clients get worse with treatment.

MBCT: MBCT works with cognitions, emotions, and sensations, some of which are distressing and difficult; they include a variety of exercises, which can be uncomfortable; and they place the formal practice of meditation at their core. It is possible that some participants receiving MBCT may get worse. A few studies have shown worsening symptoms in MBCT; however, meta-analyses consistently report significant benefits for many outcome variables in a wide range of samples. The few reviews including data on AEs and SAEs in evidence-based mindfulness practices report that they have occurred in zero to 10.6% of participants, are no more common in than in comparison conditions, and are not clinically significant.

Symptom / Behavioral Measurements: There are minimal risks involved in the collection of symptom and behavioral data. It is unlikely, but possible, that subjects may become frustrated by completing the tasks; and/or distressed at recollecting or reporting on difficult emotional experiences.

MRI: Study participants will participate in MRI scans that they would not have otherwise. The risks in this study associated with MRI scanning are comparable to having a routine MRI exam like that performed in hospitals throughout the world. There are no known risks associated with the use of MRI *per se*, but there are two areas of concern. The first is the safety risk posed by the attraction of ferromagnetic metal objects by high strength magnetic fields. The second is the discomfort some participants encounter by the confinement within the bore of the MRI system. Both types of risks occur for all clinical MRI exams and are not increased by the proposed research.

Suicidality: As with any study that utilizes samples that may include participants with mood disorders, there is the potential risk that a participant's mood may worsen, and/or that a participant may become suicidal. PI [name] and the rest of the CBRTTP staff have extensive experience working with suicidal populations. Suicidal ideation will be assessed at the initial interview and self-report session and as indicated throughout the study. Suicidal ideation will be assessed at each research assessment session and as indicated throughout the study using the Columbia-Suicide Severity Rating Scale (C-SSRS) screening interview. Participants indicating "yes" on items 4 (Active Suicidal Ideation with Some Intent to Act, without Specific Plan) and/or 5 (Active Suicidal Ideation with Specific Plan and Intent) within the last week will be excused from the trial and referred to more intensive clinical management. As a part of that risk assessment and plan, an ideographic safety plan will be developed that may include a safety contract, referral for further outpatient treatment, and/or inpatient hospitalization.

Incidental Findings: On rare occasions, a participant may exhibit a frank abnormality on their research MRI scan as noted by the research MRI technician. In consultation with our Office for Risk Management, we have developed the following protocol for these infrequent events: (1) the MRI technician will inform the center director and/or associate director and the PI of the finding, and they will evaluate the images for technical artifacts; (2) if no technical artifacts are present, the anatomical images will be examined by a neuroradiologist who will evaluate the images and provide a follow-up recommendation. Because images are not of clinical quality, a definitive diagnosis is not possible; (3) If the incidental finding is within normal limits, no further action will be taken. (4) If the finding is not within normal limits, the participant will be contacted by phone by the PI and will given a letter that provides additional explanation and reference materials. The PI will follow-up by telephone to ensure that the process has been completed and that the participant does not have further questions.

Pregnancy: Although MRI poses no known risks to fetuses, pregnant woman will be excluded from participation according to UNC IRB policy that requires that all female research subjects of childbearing potential be given a urine pregnancy test immediately prior to the MRI scan session to rule out pregnancy.

Protections Against Risk

Symptom / Behavioral Measurements: To minimize the risk of a participant becoming stressed, the laboratory space will be designed to be patient-friendly. Breaks will be provided as requested, and assessors will be flexible in the pace and scheduling of assessments.

Treatment/Suicidality. Care will be taken to assure that no participant will be in danger of harming themselves. Any participant who reports suicidal intent will be immediately assessed using the Suicide Risk Assessment protocol. Based on the level of assessed risk, patients may be escorted to the Emergency Room for further evaluation. Participants who report a significant increase in psychiatric symptoms including suicidality will be

excused from the research protocol and referred for more extensive treatment, including referral for medications, if desired. Following the conclusion of the trial, all participants will be provided with referral information as appropriate for further treatment.

MRI: This MRI studies follow guidelines with regard to specific absorption ratio (SAR) and limits on gradient slew rate (dB/dt). Participants will be interviewed and will fill out a screening questionnaire for 7T imaging safety prior to entering the MRI suite. Participants will be instructed to remove all metal objects, including clothing with metal clasps, before entering the magnet room. Some participants may feel uncomfortable or confined once positioned within the MRI system. This potential reaction will be reduced by discussing the procedure prior to entry, by providing the participant with a mirror through which they can look out into the room, and by communicating with the participant over the intercom.

Confidentiality: To protect confidentiality, only alphanumeric ID numbers, rather than names, will appear on clinically sensitive charts and digital data. The key linking the alphanumeric identifier and participant's identity will be maintained on a separate drive that will be double password protected and to which only the PIs and key study personnel will have access. All research personnel will have completed HIPPA training for researchers and CITI training.

Potential benefits of the Proposed Research to Human Subjects and Others: The primary benefit of this study will be the validation of a novel treatment for anhedonia as well as the collection of new information regarding clinically significant problems with anhedonia.

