4.5 Concomitant Medication documentation

At study entry, subjects may not have taken any psychotropic medications in the past 4 weeks (8 weeks for fluoxetine). At each therapy visits participants will be asked to report any medications they may have initiated, and any psychotropic medication use will be exclusionary. Concomitant medications will be documented in RedCap.

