6.4 Statistical Methods

Aim 1, fMRI outcomes: Only patients who complete at least two therapy sessions will participate in post-treatment assessments. We will compare fMRI activation in regions of interest at pre- and post-treatment. The design is a 2 (BATA vs MBCT) X 2 (CN, rACC) X 2 (pretreatment vs post-treatment) ANCOVA testing the change from pre- to post-treatment as moderated by treatment group and brain region in the outcome variables. The Treatment × Time interaction beta will be used to evaluate whether BATA produces changes in neural responses to reward anticipation and reward outcomes that exceed our *a priori* target engagement criteria (increased right caudate nucleus (CN) activation during reward anticipation and decreased rostral anterior

cingulate cortex (rACC) activation during reward outcomes) and exceed changes due to MBCT. *Post-hoc* comparisons will compare change across each region.

Aim 2, anhedonia outcomes: To evaluate the effects of BATA, relative to MBCT, for on anhedonia symptoms treating anhedonia, we will test for differential change over time between those who receive BATA and those who receive MBCT post-treatment. We will use an intent-to-treat (ITT) analysis for patients who receive BATA relative to those who don't. The ITT model will be a repeated-measures ANCOVA with effects for treatment condition (BATA, MBCT), outcome measure (SHAPS), time (pre-treatment, post-treatment) and their interactions. The interaction tests will assess mean differences at each time point as well as differences in the degree of change between the groups. This also provides tests of each group relative to their baseline scores. We will include gender and age as covariates in these models.

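### Aim 2 is labelled intent-to-treat, but no SHAPS is scheduled after a patient is removed for worsening, patients with fewer than two sessions are barred from post-treatment assessment, and the week 8 and 12 SHAPS are not used

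*Combined protocol and SAP*

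**What the plan says.** **Removal rules.**
- Section 1.3, Potential Risks (Suicidality): a patient positive on C-SSRS item 4 or 5 "within the last week will be excused from the trial and referred to more intensive clinical management". On timing, "Suicidal ideation will be assessed at each research assessment session and as indicated throughout the study".
- Section 1.3, Protections Against Risk: "Participants who report a significant increase in psychiatric symptoms including suicidality will be" taken out of the study. In full, the consequence for such patients is to be "excused from the research protocol and referred for more extensive treatment, including referral for medications, if desired".
- Section 4.5: for medication started during therapy, "any psychotropic medication use will be exclusionary". It does not say what such patients are excluded from; removal from the study is the most natural reading.
- Section 5.3 adds withdrawals for distress or refusal, a newly disclosed contraindication, or a positive pregnancy test.
- Section 4.7 defines dropout as three consecutive missed appointments and says the definition will be used in analyses. It does not say how, and it does not mention excused patients.

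**Outcome collection.**
- Section 4.2 schedules SHAPS at pre-treatment, week 8, week 12 and post-treatment.
- Section 6.4, under Aim 1: "Only patients who complete at least two therapy sessions will participate in post-treatment assessments". The synopsis repeats this.
- Section 4.3 (follow-up) offers only referral information.

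**Analysis.**
- Section 6.4, Aim 2: "We will use an intent-to-treat (ITT) analysis for patients who receive BATA", contrasted with those who do not receive it.
- The model is a repeated-measures ANCOVA with two time levels, pre and post, adjusted for gender and age. It is also said to test each group against its own baseline.
- No estimation or missing-data method is named.
- Section 6.2 defines the secondary endpoint as the difference between arms in change over time.

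**The concern.** An intent-to-treat analysis needs an outcome for every randomised patient, or a stated way of handling its absence. Here the protocol's own rules remove patients because they have got worse and are silent on their later SHAPS. Such a loss is plausibly related to the outcome.

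The two-time-point model adds to the problem. Fitted to complete pairs, it drops anyone without a post score. Fitted by likelihood, it keeps baseline-only patients but infers their post score from patients who were not removed for worsening. In both cases the week 8 and 12 scores, which may be the last information on a removed patient, are unused.

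At stake are mainly the within-arm changes and the meaning of the intent-to-treat label. The label is also weakened by the two-session bar and by wording that groups patients by treatment received.

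**Working it through.** The documents give no SHAPS standard deviation, removal rate, dropout rate or power figure for Aim 2, so there is no stated figure to reproduce. The size can only be shown under assumptions.

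**Inputs**
- 60 randomised, 30 per arm (synopsis).
- Removed for worsening without a post score: p = 3% to 10%. This is assumed. Section 1.3 gives 3% to 10% as the general share of psychotherapy clients who get worse, which is not a removal rate. It would mean 0.03 × 60 = 1.8 to 0.10 × 60 = 6 patients.
- The worst on a normally distributed trigger are removed, and the trigger correlates rho with SHAPS change. Rho is unknown, so 0, 0.5 and 1 are shown.
- Medication starters, ordinary dropouts and section 5.3 withdrawals are not in the figures, because the documents give no rate for them.

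**Complete pairs only.** Shift towards improvement within an arm, in SD of SHAPS change = rho × phi(z) / (1 − p), where z cuts off the worst fraction p.
- p = 0.03: z = 1.881, phi = 0.0680, 0.0680 / 0.97 = 0.070.
- p = 0.10: z = 1.282, phi = 0.1755, 0.1755 / 0.90 = 0.195.
- At rho = 0.5 these halve to 0.035 and 0.098. At rho = 0 both are zero.

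**Likelihood fits.** Simulated with 1.5 million draws per case, pre-post correlation 0.3 to 0.7, and exchangeable or time-decaying correlation. For the four-time-point fit, removal time was uniform over 15 weeks.

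| Analysis | 3%, rho 0.5 | 3%, rho 1 | 10%, rho 0.5 | 10%, rho 1 |
|---|---|---|---|---|
| Complete pairs | 0.035 | 0.070 | 0.098 | 0.195 |
| Likelihood, pre and post | 0.023–0.030 | 0.048–0.061 | 0.065–0.084 | 0.141–0.173 |
| Likelihood, all four times | 0.019–0.027 | 0.039–0.056 | 0.052–0.075 | 0.115–0.159 |

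Under this mechanism the interim scores help modestly, and most of the gain must come from obtaining the post score. If removal instead depends only on the observed week 8 change, a fit using week 8 removes the bias. In a separate simulation with 3% removed in one arm and 10% in the other, and correlation 0.6 over 8 weeks, a contrast bias of about 0.09 (in SD of a single SHAPS score) fell to 0.00.

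**If some removed patients already have a post score** (for example, identified at the post-treatment session), the complete-pairs figures at 10% fall. With a quarter already scored they are 0.071 (rho 0.5) and 0.142 (rho 1). With half already scored they are 0.046 and 0.092.

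**Difference between arms.** With equal removal rates and equal rho the shifts cancel. At 10% in one arm and 3% in the other:
- Complete pairs: 0.195 − 0.070 = 0.125 at rho 1, and about 0.062 at rho 0.5.
- Likelihood, pre and post: 0.141 − 0.048 = 0.093 to 0.173 − 0.061 = 0.112 at rho 1; 0.042 to 0.054 at rho 0.5.
- For scale, the standard error of the contrast with 30 per arm is sqrt(2/30) = 0.26 SD.

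**The case against.** **The stated endpoint is not shown to be harmed.** A reader might infer that the BATA versus MBCT comparison on SHAPS is biased. The documents do not support that. It would need removal, or its link to SHAPS, to differ by arm, and section 1.3 reports adverse events in mindfulness practices as no more common than in comparison conditions. Even at 10% against 3%, the shift is about a quarter to a half of the standard error. This stands.

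**The size is assumed.** The triggers are C-SSRS items and an undefined increase in symptoms, not anhedonia measures, and the range includes zero. This also stands.

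**Follow-up is not forbidden.** A reader might infer that excused patients may not be assessed. Apart from the two-session bar, the text is silent. That rule makes sense only if some non-completers do attend post-treatment assessment, and scheduling SHAPS immediately after treatment could be read to cover an early end. Yet the rule sits under Aim 1 and says nothing of excused patients, the visit table ties the last SHAPS to the final visits, and being excused from the trial points the other way. One sentence would settle it.

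**Pre/post is a legitimate choice, and the interim scores add little.** The first part is fair: the week-15 contrast can remain the target. The gain from weeks 8 and 12 depends on the removal mechanism. Under the uniform-timing assumption it is at most about 0.05 SD (10%, rho 1, pre-post correlation 0.7, decaying correlation: 0.173 against 0.128). The scores are already scheduled.

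**Scores after removal may reflect other treatment.** True. A result without them is needed beside the main one, and that result brings back some of the selection. This limits the gain but does not remove it.

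**Conclusion.** The concern holds as a mismatch between the label and the data the plan would collect. Aim 2 is called intent-to-treat, yet patients excused for worsening or suicidality, and probably those who start psychotropic medication, have no SHAPS scheduled after removal. Patients with fewer than two sessions are barred from post-treatment assessment, and two scheduled SHAPS time points are left out of the model.

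Under assumed removal of 3% to 10%, within-arm improvement may look too favourable by up to about 0.07 SD (3%) to 0.2 SD (10%), and by nothing if the trigger is unrelated to SHAPS. Those upper limits need complete-pairs analysis, a trigger that tracks SHAPS change perfectly, and no post score for anyone removed.

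No bias is shown in the between-arm endpoint of section 6.2, and nothing here concerns the fMRI endpoint. Nor does every excused patient lack data: some would already have a post score or an interim one, and anyone excused before randomisation never enters the analysis. This is a cheap improvement to a secondary analysis, worth making because outcomes not collected at the time cannot be recovered later.

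**What to change.** Keep every clinical safeguard unchanged, and make these changes.

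1. State in sections 1.3, 4.5, 4.7 and 5.3 that leaving therapy does not end SHAPS collection for any randomised patient. This covers those excused for worsening or suicidality, medication starters, section 5.3 withdrawals, section 4.7 dropouts and those with fewer than two sessions. Lift the two-session rule for SHAPS, and say what section 4.5 excludes medication starters from.
2. With consent, obtain SHAPS (14 items, by computer) at exit and at the scheduled post-treatment date.
3. In section 6.4, analyse by randomised arm rather than by treatment received. Use a likelihood-based longitudinal model with all four SHAPS time points, keep gender and age as covariates, and take the week-15 treatment-by-time contrast as the Aim 2 result.
4. Flag scores taken after referral or medication, and show a sensitivity result without them.
5. Report removals by reason and arm beside the Aim 2 result.

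**Cost.** A few clarifying sentences, a consent line if the consent form does not already cover this (the consent pages are not in the documents reviewed), and one or two short questionnaires per patient who leaves early. That is about 2 to 6 patients excused for worsening under the assumption, plus medication starters, withdrawals and ordinary dropouts, for whom no rate is given. The week 8 and 12 scores are already scheduled. The main downside is that some scores will reflect treatment received elsewhere.
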